12.b. Definition of Adverse Events and Protocol Deviations.

12.b.1. Definition of adverse events (AE) for this study. Any undesirable sign, symptom or medical or psychological condition that is related to the study intervention (cognitive behavioral therapy).

12.B.2 Definition of serious adverse event. A serious adverse event will be considered any undesirable sign, symptom, or medical condition which is fatal, is life-threatening, requires or prolongs inpatient hospitalization, results in persistent or significant disability/incapacity, constitutes a congenital anomaly or birth defect, is medically significant and which the investigator regards as

serious based on appropriate medical judgment. An important medical event is any AE that may not result in death, be life-threatening, or require hospitalization but may be considered an SAE when, based upon appropriate medical judgment, it may jeopardize the patient and may require medical or surgical intervention to prevent one of the outcomes listed in the definitions of SAEs.

12.b.3 Definition of an unanticipated problem. An unanticipated problem is any event, experience that meets ALL 3 criteria below (*see MUSC IRB policy HRPP 4.7*):

- is unexpected (in terms of nature, severity, or frequency) given: (a) the research procedures that are described in the protocol-related documents, such as the IRB-approved research protocol and informed consent document; and (b) the characteristics of the subject population being studied;
- is related or possibly related to a subject's participation in the research; and
- suggests that the research places subjects or others at a greater risk of harm (including physical, psychological, economic, or social harm) related to the research than was previously known or recognized.

12.b.4 Definition of a protocol deviation. A protocol deviation is any variance from the protocol involving a subject or subjects that is not approved by the IRB prior to its initiation or implementation, and occurs when a member of the study team departs from the IRB-approved protocol in any way without the investigator first obtaining IRB approval (*See MUSC IRB Policy HRPP 4.14*).

12.c. Adverse Event / Unanticipated Problem Recording and Reporting.

12.c.1. Inclusivity of adverse events collection. All AEs described above will be collected and reported.

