12.c.2. Method of event data collection. Data collection will occur via electronic spreadsheet. The information will be saved in REDCap and managed by the study team.

12.c.3. Adverse Event classification. AE classification will occur using NCI Common Toxicity Criteria, Version 4.0.

12.c.4. Relationship of adverse events to study participation. The PI will specify the following relationship of AEs to study participation:

- | | |
|-----------|---|
| Definite: | AE is clearly related in time and a direct association can be demonstrated to the study intervention |
| Probable: | AE is reasonably related in time and is more likely explained by the study intervention than by other causes |
| Possible: | AE may be reasonably related in time and the AE can be explained equally well by causes other than the study intervention |

12.c.5. Timing of recording/reporting of adverse events/unanticipated problems.

Recording/reporting of AEs will begin after the subject signs informed consent and end after the subject completes the intervention and follow up period as defined in the protocol.

12.d. Data and Safety Oversight Responsibility.

12.d.1 Persons responsible for overseeing safety data. The PI will be responsible for overseeing safety data.

12.d.2. Content of aggregate reviews. Aggregate reviews will occur by the PI for all adverse events, unanticipated problems, protocol violations, audit results, early withdrawals, whether the study accrual pattern warrants continuation/action, and endpoint data.

12.d.3. Timing of aggregate reviews. Aggregate reviews will occur monthly.

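### The AE definition admits only events related to CBT and the causality scale stops at Possible, while the SAE definition carries no such limit, so unrelated events have no clear place in the safety record

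*Protocol*

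**What the plan says.** All of this is in Protocol section 12.0.

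- **AE definition (12.b.1):** "Any undesirable sign, symptom or medical or psychological condition that is related to the study intervention (cognitive behavioral therapy". Relatedness is part of what makes an event an AE.
- **Collection (12.c.1):** "All AEs described above will be collected and reported". No wider collection is stated.
- **SAE definition (12.B.2):** "A serious adverse event will be considered any undesirable sign, symptom, or medical condition which is fatal, is life-threatening", followed by the other usual seriousness criteria. This sentence has no relatedness condition and does not mention psychological conditions. The paragraph then describes an important medical event as a kind of AE, which brings the 12.b.1 condition back in.
- **Unanticipated problems (12.b.3):** three criteria must all be met. One is that the event "is related or possibly related to a subject's participation in the research; and" the others are that it is unexpected and that it points to greater risk than was known.
- **Causality (12.c.4):** "The PI will specify the following relationship of AEs to study participation". The grades are Definite, Probable and Possible. Possible is worded as "AE may be reasonably related in time and the AE can be explained equally well by causes other than the study intervention".
- **Oversight (12.d.1):** "The PI will be responsible for overseeing safety data". The PI also carries out the monthly aggregate reviews (12.d.2, 12.d.3).

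**The concern.** Causality is normally assessed after an event has been recorded. Here it is a condition of recording, and the later grading step covers only events that have already passed it.

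This matters more than usual in this trial. Participants are enrolled because they have body image disturbance after cancer treatment (5.c.1). The expected risks listed in 12.a.1 are emotional distress or discomfort and frustration, and 14.a adds that participants may be upset by talking about cancer or body image. The likely harm of the intervention therefore looks much like the condition being treated. The design is single-arm (10.a), so no comparison group can separate the two, and event-by-event attribution is least reliable exactly where it decides what is recorded. Section 15.b says the data should support a later randomized trial, which would inherit whatever harm profile this study reports.

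**Working it through.** The protocol states no safety figure to reproduce. The main check sets the clauses side by side for four kinds of event.

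| Event | AE under 12.b.1? | SAE under 12.B.2? | Collected under 12.c.1? | Grade in 12.c.4? |
|---|---|---|---|---|
| Non-serious, CBT at least as good an explanation as any other | Yes, if related is read to include possibly related | No | Yes, on that reading | Possible or higher |
| Non-serious distress put down mainly to the cancer | No | No | No | None fits |
| Hospitalization judged unrelated to CBT | No | Yes, by the main sentence | Unclear: the clause says AEs, and this is not one | None fits |
| Important medical event judged unrelated | No | Conflict: the main sentence includes medically significant events, but the closing sentence requires an AE | Unclear | None fits |

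Three inconsistencies follow.

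1. **Scope.** SAEs are not limited by relatedness in the main sentence of 12.B.2, but AEs are in 12.b.1. An unrelated SAE is then an SAE that is not an AE.
2. **Threshold.** 12.b.1 requires that the event is related, 12.b.3 accepts possibly related, and the lowest grade in 12.c.4 accepts an equally good alternative explanation. The clauses do not share one cut-off.
3. **Kind of harm.** 12.b.1 names psychological conditions and 12.B.2 does not, although both risks listed in 12.a.1 are psychological.

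**Illustration of size.** The only protocol input is n = 20 (6.0). The share of participants with an undesirable non-serious event, p, and the share of those events judged related, q, are assumptions. Take at most one event per participant and independence between participants. Then

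- expected participants with a recorded event = 20 × p × q
- chance that none is recorded = (1 − p × q)^20

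For p = 20%, the expected number is 4, 3, 2 and 1 for q = 100%, 75%, 50% and 25%. The chance of recording none is:

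| p | q = 100% | q = 75% | q = 50% | q = 25% |
|---|---|---|---|---|
| 10% | 12.2% | 21.0% | 35.8% | 60.3% |
| 20% | 1.2% | 3.9% | 12.2% | 35.8% |
| 30% | 0.1% | 0.6% | 3.9% | 21.0% |

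For example, p = 20% and q = 50% gives (1 − 0.10)^20 = 0.122, against (1 − 0.20)^20 = 0.012 with no filter.

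**The case against.** The best defense is that the scheme is coherent for non-serious events: if an AE is related by definition, an unrelated grade has no use. Restricting collection in this way can be a deliberate choice for a talking therapy with no physical risks (14.a) and with listed risks marked as rare (12.a.1). Possible is also a generous grade, so distress for which CBT and the cancer are equally good explanations can be recorded. This stands as a limit on how much is lost, but it does not help with SAEs, where the clauses disagree.

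There are other routes into the data. PROMIS depression and anxiety are measured (4.c.2), unanticipated problems include psychological harm (12.b.3), and the monthly review covers unanticipated problems, early withdrawals and endpoint data as well as AEs (12.d.2). So capture is partial, not nil. Scheduled scores are not event records, however, and distress already listed as an expected risk would often fail the unexpectedness criterion.

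The SAE wording can also be read more kindly. A symptom may be psychological, and the collection clause follows both definitions, so it may be meant to include SAEs. That makes these two points ambiguities to settle rather than proven omissions.

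Two stronger readings are tempting. A reader might infer that the PI decides what is written down and so fixes the safety result. The protocol does not say so: it names the PI as grader and overseer, has the study team manage the records (12.c.2), and does not say who judges relatedness before entry. A reader might also attach an upper bound to a report of no AEs; for 0 of 20 the exact one-sided 95% bound is 1 − 0.05^(1/20) = 13.9%. Safety is not an endpoint in 4.0 and section 11 plans no AE rate, so that bound answers a statement the protocol never makes.

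**Conclusion.** The point holds as a defect in the safety-recording rules. Followed as written, 12.b.1 and 12.c.1 keep non-serious events judged unrelated out of the AE record. The main sentence of 12.B.2 creates SAEs that are not AEs, are not clearly collected and have no fitting grade. The direction of any bias is toward fewer reported harms.

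Its size cannot be derived from the protocol, because neither the event rate nor the share judged related is given. Over the assumed ranges the filter can materially change what a 20-participant study reports, with the chance of recording no event rising up to 60.3% in the most extreme combination shown. The conclusion rests on reading the collection clause literally and on some events being judged unrelated. It concerns safety reporting only and does not touch the primary BIS analysis. The change should be made, but it does not threaten the study's main result.

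**What to change.** - **12.b.1:** keep the present cover for any sign, symptom or condition related to CBT. Add any new or worsening psychological event, and any SAE, from consent to the end of follow-up, whether or not considered related. Replacing the present definition with psychological events and SAEs alone would drop non-serious, non-psychological events related to CBT that are now covered.
- **12.c.1:** state that SAEs are collected.
- **12.c.4:** add unlikely and unrelated grades.
- **12.B.2:** include psychological conditions, in line with 12.b.1, and settle whether the important-medical-event sentence depends on relatedness.

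The cost is protocol wording and two more options on the AE form. Some extra events will be recorded, possibly more than a few because participants are selected for body image disturbance, but this is manageable with n=20. Limiting the added non-serious capture to psychological events avoids logging routine cancer-treatment toxicity.

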10.0 Study Design / Methods

10.a. Study Design. The proposed study is a prospective, single institution, single-arm, phase II pilot study. Cognitive Behavioral Therapy will be implemented into the clinical care of HNC patients at MUSC and HCC. The effects of CBT on body image disturbance will be measured using the Body Image Scale and analyzed using a pre- and post- study design.

10.b. Study Intervention

10.b.1. Development of a CBT Module for HNC Patients with BID. Although extensive literature exists for implementation of disorder-specific CBT³⁹, no specific CBT modules for HNC patients with BID exist. Therefore a critical initial step is to establish a disorder-specific CBT intervention for HNC patients with BID. In conjunction with [name], [name] will develop a 5-week, CBT module for HNC patients with BID using CBT core components (i.e. psychoeducation, self-monitoring, and cognitive restructuring). The intervention will be informed by existing CBT from other body image disorder realms^{40,41}. The intervention will contain population-specific components including identifying and modifying maladaptive beliefs about disfigurement and functional changes following surgery. It will address the multidimensional nature of BID in HNC patients⁶ and will seek to reduce avoidance behaviors, improve social support, and enhance adaptive stress management skills.

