10.b.2. CBT Intervention and Implementation. At the 1-month post-HNC treatment time point, patients with BID as determined by BIS score ≥ 5 will undergo time-limited CBT consisting of 5 weekly sessions. Each session will be guided by the HNC BID module that we develop, but customized to each patient's specific concerns⁴⁰. Each session will last ~60 minutes and be conducted one-one with [name], who will administer the CBT as part of clinical psycho-oncology care at HCC. Patients will complete questionnaires prior to CBT and 1 and 3 months after CBT (**Figure 3**). We considered alternate dose schedules of CBT but chose a 5-week schedule because evidence suggests that brief (e.g. 5-week) CBT reduces anxiety and depression and improves QOL in cancer patients⁵⁸. To overcome the expected travel distance-related barrier to receipt of CBT, we will offer the option of home-based, telemedicine CBT through an existing MUSC program⁵⁹. This will consist of one CBT session at HCC followed by iPad-based, tele-CBT for the next 4 sessions. Patients will receive the iPad and brief training session from MUSC Center for Telehealth staff at the in-person CBT session. They will take the iPads home, use them for the next 4 tele-CBT sessions, and mail them back to MUSC at the study conclusion.

10.b.3. Standardization and Treatment Fidelity. Standardization of intervention administration is critical for study validity and reproducibility. All CBT will be delivered by one psycho-oncologist (SM) with standardized content (regardless of whether the modality is in-person or tele-health CBT). To ensure fidelity of the intervention, the study psycho-oncologist will keep an intervention tracking log which captures data fields such as patient attendance at the session, CBT content delivered, completion of patient homework, technical problems with the session, rating of session length, patient engagement, and patient comprehension (to be completed by psycho-oncologist), and session duration,

10.c. Study Variables

10.c.1 Antecedent Variables.

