11.0 Data Management

11.a. Data Analysis Plan for Primary Endpoint. The primary endpoint is BIS scores measured at specific time points (Figure 3). We will summarize BIS at each time point by estimating mean and corresponding 95% confidence intervals (CIs), median, standard deviation (SD), inter-quartile range, and range. We will also construct boxplots and spaghetti plots of serially collected BIS scores to provide visual assessment of temporal changes in BIS. Finally, we will analyze BIS scores over time using linear mixed effects (LME) regression models with time as a fixed effect (considered as categorical variable) and subject-specific random effects to account for the correlation among measures obtained from the same subject over time. We will consider transformations for BIS scores to induce approximate normality and stabilize variance. BIS comparisons over time will be conducted using model-based linear contrasts. We will also consider Wilcoxon sign rank tests to compare BIS scores if variable transformations of BIS fail to induce approximate normality. We will not be specifically controlling for telemedicine vs face-to-face CBT but have planned subset analyses to see if differences exist based on method of CBT delivery.

11.b. Power Analysis/Sample Size Justification. Power analyses were performed using PASS 2008, version 08.0.13. Based on our preliminary data, we expect 35 patients/year to be eligible for the study, of

whom 84.6% will be 'somewhat likely' or 'highly likely' to participate in an intervention for their BID (unpublished data). Assuming that we enroll two-thirds of the eligible and 'likely to participate' subjects, if we enroll over 12 months, we would achieve our sample size of $n=20$.

The study seeks to characterize the effects of CBT on BID. **Figure 4** shows the power to detect absolute differences in BIS for $n=20$ based on a paired t-test with SD (BIS difference) = 3.8 (preliminary data), and two-sided $\alpha = 0.05$. We estimate power to be at least 80% to detect a difference in BIS scores of

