11.d. Steps to Maintain Confidentiality. To help protect participant confidentiality, we will assign a unique study ID number to each subject's information in place of his/her name and will label data collection forms with the ID number. All hard copy and electronic files will be stored appropriately using double-locked methods and password-protection. Only the study team member will have access to study records. Participant data will be collected and recorded on either a password-protected electronic data capture format (REDCap) or paper-based forms depending upon patient preference. For the paper collection data method, the data collection form will be labeled only with the participant's unique study ID number, and then stored within locked drawers in a locked office. The information on these paper forms will be transferred to a password-protected REDCap database such that all data will be stored in the password-protected REDCap Database. Only members of the study team will have access to the data. We have no plan to use laptops, jump drives, CDs/DVDs to transport data.

11.e Quality Control of Collected Data. The PI will meet with the study coordinator once each month to review the quality of the collected data, assessing for missing data, internally inconsistent data, other data irregularities, progress towards enrollment.

12.0 Provisions to Monitor the Data to Ensure the Safety of Subjects (if applicable)

12.a.1. Identification of risks and plans to minimize risk.

Expected Risks related to cognitive behavioral therapy	Frequency

 Emotional distress/discomfort 	 Occurs frequently,  Occurs infrequently  Occurs rarely  Frequency unknown

 frustration 	 Occurs frequently,  Occurs infrequently  Occurs rarely  Frequency unknown

12.a.2. Criteria below under which an individual subject's study treatment or study participation would be stopped or modified. At subject, PI, or study team member request.

12.a.3. Criteria under which the entire study would need to be stopped. Per IRB or PI discretion.

12.a.4. Reporting of subject withdrawals/dropouts to the IRB prior to study completion. Via IRB annual continuing renewal submission.

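### Does the PI's monthly review of endpoint data, together with discretion to stop, undermine the single test at n=20 in Protocol 11.b?

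*Protocol*

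**What the plan says.** Section 12.d.2 lists what the PI reviews in aggregate. The list ends with "early withdrawals, whether the study accrual pattern warrants continuation/action, and endpoint data". Section 12.d.3 sets the frequency: "Aggregate reviews will occur monthly". Section 12.d.1 names the person in charge: "The PI will be responsible for overseeing safety data".

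Section 12.a.3 deals with stopping the study: "Criteria under which the entire study would need to be stopped. Per IRB or PI discretion". It gives no further criterion.

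Section 11.e describes another monthly activity: "The PI will meet with the study coordinator once each month to review the quality of the collected data".

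The design in 10.a is plain: "The proposed study is a prospective, single institution, single-arm, phase II pilot study". Section 10.b.2 fixes the measurements: "Patients will complete questionnaires prior to CBT and 1 and 3 months after CBT". Section 11.b sizes the study at n=20, "based on a paired t-test with SD (BIS difference) = 3.8 (preliminary data), and two-sided" alpha of 0.05, and states at least 80% power for a BIS difference of about 2.5. Section 11.a gives the actual analysis: a linear mixed model with time as a categorical effect, and contrasts between time points.

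**The concern.** With one arm there is no allocation to mask, so anyone who sees the pooled BIS change sees the treatment effect. The PI receives endpoint data every month and may end the study without a written criterion. Section 11.e already covers missing and inconsistent data, so it is natural to read the endpoint data in 12.d.2 as results and not merely as completeness.

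If enrolment were ended because BIS looked good, the final test would no longer be the fixed-sample test of 11.b. The false-positive rate would rise, the sample would shrink, and the estimated change would tend to be too large. Section 15.b intends these data to support a randomised trial, so an inflated estimate could carry over into its planning.

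**Working it through.** **1. The power figure in 11.b.** Inputs from 11.b: n = 20, SD of the BIS difference = 3.8, two-sided alpha = 0.05, difference = 2.5.

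- Standard error = 3.8/√20 = 0.85.
- Noncentrality = 2.5/0.85 = 2.94, with 19 degrees of freedom.
- Power from the noncentral t distribution = 79.7%. The difference that gives exactly 80% is 2.51.

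The stated figure is reproduced. It holds for one analysis on 20 patients.

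**2. Does any section depart from one analysis on 20 patients?**

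- 11.a and 11.c describe the analyses and contain no interim test.
- 12.d.2 mentions continuation once, and the ground it gives is the accrual pattern. Endpoint data is a separate item in the list, with no decision attached.
- 12.a.3 belongs to Section 12.0, which is about protecting subjects. It stands beside the table of expected risks and the criteria for individual subjects. Its heading asks when the study would have to stop, and a favourable BIS trend creates no such need.
- Emotional distress is a listed risk of the intervention, so worsening BIS bears on safety. That gives the review of endpoint data a purpose of its own.

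The sections are compatible. Looking at data without acting on it does not change the error rate: a single test at n = 20 gave 5.1% in 200,000 simulated null trials, which is the nominal 5% up to simulation error.

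**3. What if the PI did stop on favourable BIS?** The protocol does not say this, so the looks are assumed.

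- Accrual (11.b): 35 × 0.846 × 2/3 = 19.7 patients in 12 months, about 1.6 per month.
- Outcome (10.b.2): available 5 weeks plus 1 or 3 months after enrolment.
- Rule: monthly looks during accrual. Enrolment stops at the first two-sided p < 0.05, and everyone enrolled completes follow-up and enters the final t-test. There were 400,000 simulated trials per scenario.

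False-positive rate with no true change, over first looks at 3, 6 or 10 patients:

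| Outcome | Stop in either direction | Stop for benefit only |
|---|---|---|
| 1 month | 6.5-7.5% | 5.8-6.2% |
| 3 months | 5.4-5.9% | 5.2-5.4% |

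In the benefit direction alone, benefit-only stopping gives 2.7-3.7% against 2.5%. Rates of 18-20% appear only if patients already enrolled but not yet measured are left out of the analysis, and half of those are claims of harm. Nothing in the protocol suggests leaving them out.

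True change 2.5, SD 3.8, stopping for benefit only (rows with a first look at 10 come from a separate run of 200,000 trials):

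| Outcome, first look | Stopped early | Mean n | Power | Mean estimate | Mean in stopped trials |
|---|---|---|---|---|---|
| 1 month, n=3 | 75% | 13.8 | 0.71 | 2.73 | 3.08 |
| 1 month, n=6 | 74% | 14.7 | 0.74 | 2.67 | 3.02 |
| 1 month, n=10 | 72% | 15.9 | 0.77 | 2.62 | about 3.0 |
| 3 months, n=3 | 61% | 16.2 | 0.75 | 2.61 | 3.01 |
| 3 months, n=6 | 58% | 17.0 | 0.77 | 2.59 | 3.01 |
| 3 months, n=10 | 54% | 18.5 | 0.79 | 2.54 | about 3.0 |

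For first looks at 3 or 6 patients, the average overestimate runs from 2.59 − 2.5 = 0.09 to 2.73 − 2.5 = 0.23. At 10 patients it is 0.04-0.12. The standard error at n = 20 is 0.85.

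**The case for a change.** The strongest contrary case starts from the text. The same person sees the accumulating effect each month and may end the study, no independent monitor is named in 12.d, and the wording does not exclude a stop for benefit. On this view the protocol itself opens the route, so the point is more than a detail left to an analysis plan. The stakes under that behaviour go beyond alpha: power could fall to 0.71, and the estimate in stopped trials would be about 3.0-3.1 for a true 2.5, roughly 20% too high. BIS has no validated clinically meaningful difference (10.c.2.a.1), so more weight falls on the size of the estimate.

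The description of the text stands, and so do the conditional figures. The inference does not. Every figure depends on a decision rule that appears nowhere in the protocol, and the larger ones depend on acting on t-tests in as few as 3 patients. A statement that no efficacy stop is intended is commonly placed in a statistical analysis plan, which was not available here. Its absence from the protocol is not an error.

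Narrowing the review to completeness of endpoint data would also achieve little. Under 11.d the study team has access to the data, and under 11.e the PI already reviews them monthly. In an open study of 20 patients the PI cannot realistically be kept from BIS.

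**Conclusion.** The concern does not hold. The monthly review and the discretion to stop are stated as described, but neither is tied to favourable BIS results, and neither conflicts with 11.a or 11.b. Run as written, the study has one primary analysis on 20 patients, a 5% two-sided error for the test used in sizing, and 79.7% power at a difference of 2.5.

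The stress case is modest. Under assumed monthly stopping for benefit with complete follow-up, two-sided error is 5.2-6.2% and the average overestimate is about 0.1-0.2 BIS points. The loss of sample and power is larger, but it belongs to a procedure that the protocol does not contain.

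The stress figures assume even accrual over 12 months and use the t-test of 11.b, not the mixed model of 11.a, so they indicate size only. The conclusion that error and power hold does not depend on them. It rests on the reading that no section provides for stopping on a favourable BIS result.
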